Adding predictor variables to the models is straightforward. For example, the level-3 random intercept and slope model with one predictor measured at each level is $Y_{ijk} = \beta_0 + \beta_1 X_{1ijk} + \beta_2 X_{2jk} + \beta_3 k + v_k + u_{jk} + \epsilon_{ijk}$, where $\beta_0 + \beta_1 X_{1ijk} + \beta_2 X_{2jk} + \beta_3 k$ is the fixed effect of the model and $v_k + u_{jk} + \epsilon_{ijk}$ is the random effect of the model. The fixed effect of the model specifies the overall mean relationship between the response and the predictor variables. The random effect of the model specifies how the provider and clinic specific relationships differ from the overall mean relationship. To assess the potential mediator effect, we will use the causal variable and the mediator variable as predictors in the model. To assess the cross-level interaction effects, we will add a product term to the model. For example, the model for a level-1 predictor (e.g. age) cross-level and interact with a level-2 predictor: $Y_{ijk} = \beta_0 + \beta_1 X_{1ijk} + \beta_2 X_{2jk} + \beta_3 (X_{1ijk} \bullet X_{2jk}) + u_{0jk} + u_{1jk} X_{1ijk} + \epsilon_{ijk}$. Since one of the patient-level (level-1) outcome measures is dichotomous (whether the patient adherence to follow-up diagnostic evaluation after a positive result within 9 months or not), we will add another level-1 model for the binary data:

$$\text{Level - 1: } \log [P_{ijk} / (1 - P_{ijk})] = \beta_{0jk} + \beta_1 X_{1jk}.$$

In this study, we will use the restricted maximum likelihood (**REML**) to estimate variances. REML treats the regression coefficients as unknown quantities to be estimated based on sample data and subtracts the needed degree of freedom when computing variance estimates. Since REML only allows for tests of models that differ in their variances, we will calculate the intraclass correlation (**ICC**) to access the variation in response variable across providers and across clinics prior to testing the models. At the end of the analysis, we will use the likelihood ratio test to

compare the nested models. The deviance values ($-2 \log L$) for the two models can be used to decide which model better fits the data:

$$(-2 \log L_{\text{Reduced Model}}) - (-2 \log L_{\text{Full Model}}) = \text{deviance}_{\text{Reduced Model}} - \text{deviance}_{\text{Full Model}}$$

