Statistical analyses will be conducted using Statistical Package for the Social Science (SPSS) version 23.0 and the significant level will set at alpha ≤ 0.05 .

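### REML and a deviance comparison are prescribed for the whole study, including the logit model for 9-month follow-up, where the deviance difference need not be a likelihood ratio

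*Combined protocol and SAP*

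**What the plan says.** All of this is in Section 4 (Data Analyses) of the combined protocol and SAP.

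- **Binary outcome.** One patient-level outcome is dichotomous: "whether the patient adherence to follow-up diagnostic evaluation after a positive result within 9 months or not". For it, "we will add another level-1 model for the binary data", a logit equation. No estimation method is given for that model.
- **Estimator.** The next paragraph begins "In this study, we will use the restricted maximum likelihood" and makes no exception for the logit model.
- **Limit on REML tests.** The same paragraph recognises a restriction: "Since REML only allows for tests of models that differ in their variances".
- **Model comparison.** "At the end of the analysis, we will use the likelihood ratio test" on nested models, and the deviances "for the two models can be used to decide which model better fits the data". Neither statement is limited to variance terms or to linear outcomes.
- **Intervention effect.** The opening paragraph of Section 4, written about linear mixed models, tests each added component from its estimated effect.
- **Software.** "Statistical analyses will be conducted using Statistical Package for the Social Science (SPSS) version 23.0". Neither the procedure nor the likelihood approximation is named.

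**The concern.** REML removes the fixed effects from a normal likelihood before estimating the variances. A logit mixed model has no exact counterpart. The usual analogue, residual pseudo-likelihood, linearises the outcome around the current fit and applies REML to the resulting working values. Those values and their weights depend on the fitted model, so a reduced and a full model are scored on different data. The difference in their -2 log values then has no chi-square reference and need not even have the right sign.

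The analyst therefore faces a fork. Following the REML instruction makes the deviance comparison invalid for this outcome. Using true maximum likelihood makes the comparison valid but departs from the REML instruction. As written, the two rules cannot both be followed validly for the logit model.

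At stake are comparisons of nested models for 9-month follow-up: whether provider or clinic variation is present, and whether interaction or mediation terms (Objective 4, Section 2.1) improve the model.

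**Working it through.** The documents give no sample size, ICC or deviance value, so there is no figure to reproduce. The check asks how the planned statistic behaves if the logit model is fitted by residual pseudo-likelihood.

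**Inputs from the documents.** 35 clinics (Section 1.2; the table in Section 2.2 gives 11 + 12 + 5 + 7 = 35). Alpha 0.05 (Section 4).

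**Assumed inputs.** 10, 20 or 40 patients with a positive test per clinic; follow-up of 30%, 50% or 70% without the effect; odds ratio 1, 1.3, 2 or 0.5; clinic variance 0.3 on the logit scale (0, 0.3 and 0.6 for the variance test).

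**Statistics compared.**
- Working response z = η + (y − μ)/[μ(1 − μ)] with weight w = μ(1 − μ), rebuilt at each model's own fit. The pseudo-deviance is the REML -2 log L of z.
- True ML by 20-point quadrature on the same data.
- Difference = reduced minus full. Cut-off 3.84 for one fixed effect and 2.71 for one variance.

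**Expected direction.** The pseudo-deviance contains Σ −log[μ(1 − μ)]. Its second derivative in η is 2μ(1 − μ), or 0.5 at μ = 0.5, so a model that spreads the fitted probabilities is penalised. For a within-clinic odds ratio of 2, η moves by ±ln2/2. With 35 × 20 = 700 patients the penalty is about 700 × ½ × 0.5 × (ln2/2)² = 700 × 0.25 × 0.120 = 21.

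**Results** (60 to 100 runs per setting):

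| Comparison | Pseudo-deviance: median difference | Larger model favoured | ML: larger model favoured |
|---|---|---|---|
| Within-clinic OR 2 or 0.5, 20 per clinic | −21.1 to −27.8 | 0% | 97-100% |
| Within-clinic OR 2, 10 per clinic | −10.4 | 0% | 87% |
| Within-clinic OR 2, 40 per clinic | −49.9 | 0% | 100% |
| Within-clinic OR 1.3, 20 per clinic | −4.8 | 0% | 37% |
| Between-clinic OR 2, 20 per clinic | −3.4 | 2% | 80% |
| OR 1 (no effect), 20 per clinic | −2.2 to −2.7 | 0% | 4-8% |
| Clinic variance 0.3 | −34.6 | 0% | 94% |
| Clinic variance 0.6 | −65.4 | 0% | 100% |
| Clinic variance 0 | −0.004 | 0% | 9% |

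The simulated medians for OR 2 or 0.5 are of the size the penalty predicts. The variance rows are the one kind of comparison that Section 4 itself allows for REML, and they fail too.

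**Three levels.** A small check with providers within clinics (20 clinics, 60 providers, 300 patients, OR 2, only 15 runs) gave a median of −9.2 for dropping the phase term, against a predicted penalty of 300 × 0.25 × 0.120 = 9.0. Dropping the clinic effect with the provider effect kept gave −1.9. The larger model was favoured in 0% both times.

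**Wald test from the same pseudo-likelihood fit** (35 clinics of 12, 20 or 30; clinic SD 0.7; log odds ratio 0.6; 300 runs each). It rejected in 79%, 96% and 99.7%, and in 4-5% when the log odds ratio was 0. The pseudo-deviance passed 3.84 in 0%.

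**Linear models.** For one null fixed effect (300 runs), the REML deviance rejected in 1.3%, and in 0.3% after the predictor was multiplied by 100; ML gave 6.3% and 4.7%. The REML criterion includes a determinant of the design, which rescaling shifts by 2 ln 100 = 9.21. The median difference moved from −2.88 to −12.06, a shift of 9.18. A REML deviance for a fixed effect thus depends on the predictor's units.

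**The case against.** The strongest reply is that little rests on this comparison.

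- **A reader might infer that a real phase effect would be missed.** The documents do not support that. Section 4 tests each component from its estimate, and the Wald results show that this route keeps its power. Using a REML deviance for a phase term would also contradict the plan's own words, "Since REML only allows for tests of models that differ in their variances". This stands, with two caveats: the sentence on testing from the estimate is written for linear mixed models, so applying it to the logit model is a natural reading rather than a stated one; and the Wald simulation had one random intercept and no time trend or FQHC effect.
- **A reader might infer that provider or clinic effects would be dropped.** No rule says so. Section 4 adopts multilevel modelling because of the nesting, not subject to a test. A negative nested difference is also impossible under true ML, so an analyst could notice it.
- **A reader might infer that SPSS is bound to produce this result.** The documents name no procedure or approximation, and the simulations re-implement an algorithm; they are not SPSS output.
- **A reader might infer that the rule always picks the wrong model.** With no effect, it picked the reduced model, correctly.
- **Scope.** The 9-month yes/no outcome is not listed as such in Table 2 (Section 3.5), and the plan moves no other outcome to the logit model.

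These points narrow the consequence. They do not supply a valid estimation and comparison rule for the logit model, and the deviance comparison is not restricted to linear outcomes.

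**Conclusion.** The point holds in a limited form. Section 4 prescribes an estimator and a comparison that do not carry over together to the logit model, and it offers no substitute. If that model is fitted by residual pseudo-likelihood, the deviance difference is not a likelihood ratio. In the simulations it favoured a real clinic variance in 0% of runs and a real fixed effect in 0-2%.

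The damage is confined to nested-model comparisons for the binary outcome: variance terms, shown directly, and interaction and mediation terms, which were not simulated but enter the model as fixed effects. The conclusion on the intervention is affected little, provided it is drawn from the estimate.

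This rests on a pseudo-likelihood fit, which the documents neither confirm nor exclude, and on assumed patient numbers, follow-up rates and variances. The main simulation had one clinic-level intercept; providers within clinics were covered only by the 15-run check.

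**What to change.** Reword Section 4 as follows.

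1. **Linear models.** Use REML deviances only to compare variance terms with the same fixed effects. Use ML deviances for fixed effects.
2. **Logit model.** Name the procedure and the likelihood approximation, and choose one of two routes:
   - fit by maximum likelihood with adaptive quadrature or Laplace, if likelihood-ratio tests are wanted; or
   - keep the provider and clinic effects in without testing them, use Wald or F tests of the coefficients, and make no deviance comparison.
3. **Intervention effect.** State that testing from the estimate also applies to the logit model.

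The cost is a change of wording. A second statistics package is needed only if the maximum likelihood route is chosen and SPSS cannot provide it.

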2. STUDY OBJECTIVES, DURATION, AND STUDY SITES

2.1. Study Objectives

Objective 1: *Collect baseline data during the first 6 months before implementing any intervention component.*

Objective 2: *Implement the intervention in three phases: 1) provider education plus community outreach; 2) add provider assessment and feedback + patient reminder; and 3) add a CRC navigator program.*

Objective 3: *Create a grand model to test the overall effectiveness of the multilevel intervention on primary outcomes within and across levels, as well as separate models to assess effectiveness at each phase.*

Objective 4: *Identify potential interaction or mediation effects and assess such effects on primary outcomes.*

Exploratory Objective 5: *Implement a local innovation, IL ColonCARES Program, and assess its feasibility and effectiveness on the follow-up of abnormality.*

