4. DATA ANALYSES

In order to evaluate the effect of the multilevel, multicomponent intervention, we will take a step-by-step approach. First, each intervention effect at each time phase will be estimated separately using linear-mixed effects models. The estimate of intervention effect in each model will be used to test if additional intervention component significantly affects outcome measures. Next, we will develop a grand model including all three intervention effects simultaneously in addition to the models described above.

In this study, patients are nested within providers and providers are nested within clinics. The problem with nested data structures is that they violate the independence assumption of traditional regression models. Thus, we will use multilevel modeling to analyze our data. We will start with the unconditional three-level random intercept models:

$$\text{Level - 1: } Y_{ijk} = \beta_{0jk} + \epsilon_{ijk};$$

$$\text{Level - 2: } Y_{ijk} = \beta_{0k} + u_{jk} + \epsilon_{ijk}$$

$$\text{Level - 3: } Y_{ijk} = \beta_0 + v_k + u_{jk} + \epsilon_{ijk}$$

where Y_{ijk} is the observed outcome for patient i with provider j in clinic k . β_0 is the mean response across all clinic. v_k is the random effect of clinic k , u_{jk} is the random effect of provider j , and ϵ_{ijk} is the residual error. The random effects and residual errors are assumed independent of one another.

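### Does the closing likelihood ratio test in Section 4 overstep the limit the plan itself sets on REML?

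*Combined protocol and SAP*

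**What the plan says.** Section 4 first estimates the effect of each phase in its own linear mixed model and uses that estimate to test whether the added component matters. After that, "we will develop a grand model including all three intervention effects simultaneously". The multilevel modelling starts from unconditional random-intercept models and then takes in predictors. For mediation, "we will use the causal variable and the mediator variable as predictors in the model". For interaction, "To assess the cross-level interaction effects, we will add a product term to the model".

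REML is the only estimation method named for the mixed models, and it is named for estimating variances. The plan states its limit, "Since REML only allows for tests of models that differ in their variances", and draws one consequence: intraclass correlations are calculated before models are tested. The next sentence begins "At the end of the analysis, we will use the likelihood ratio test to" and goes on to compare nested models. The difference in −2 log L between a reduced and a full model "can be used to decide which model better fits the data".

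Section 2.1 sets the aims these models serve. Objective 3 is to "Create a grand model to test the overall effectiveness of the multilevel intervention on primary outcomes within and across levels". Objective 4 is to "Identify potential interaction or mediation effects and assess such effects on primary outcomes".

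**The concern.** The plan states the rule and then describes a test without repeating it. The closing comparison names no pairs, mentions no ML fit and does not require the two models to share their fixed effects. It also comes at the end, after steps that mostly add fixed effects: predictors, a mediator, a product term and the three phase effects of the grand model. A literal reader could therefore take two REML fits with different fixed effects and refer their deviance difference to a chi-square distribution.

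That comparison is invalid. With p fixed effects in the reduced model and p + q in the full one, the two REML likelihoods rest on n − p and n − p − q error contrasts, so they are likelihoods of different data. At stake would be the final choice of model, any mediation or interaction result under Objective 4, and any joint test of the three phase effects under Objective 3, if these were judged by deviance.

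**Working it through.** The plan gives no deviance, power or sample-size figure on this point, so there is nothing to reproduce. The check has three parts.

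**1. How bad the invalid comparison would be.** The REML deviance is

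−2 log L(REML) = (n − p) ln(2π) + ln det(V) + ln det(X'V⁻¹X) + r'V⁻¹r,

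with or without a term −ln det(X'X), depending on convention. Multiplying the outcome by c adds 2(n − p) ln(c). For q added fixed effects, reduced minus full therefore moves by 2(n − p) ln(c) − 2(n − p − q) ln(c) = 2q ln(c). Under ML both models gain 2n ln(c), so the difference does not move. With c = 100 (proportion to percent):

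| Added terms q | REML shift, 2q ln(100) | ML shift | 5% critical value |
|---|---|---|---|
| 1 | 9.21 | 0 | 3.84 |
| 2 | 18.42 | 0 | 5.99 |
| 3 | 27.63 | 0 | 7.81 |

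The shifts need no assumed inputs. A numerical fit returned the same values under both REML conventions. It used the plan's 35 clinics and 60 + 21 + 35 + 20 = 136 providers (Section 2.2) over 16 quarters, 136 × 16 = 2,176 records, with assumed variance components.

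The level of the difference, unlike the shift, does depend on assumptions. An illustrative simulation used 35 clinics, with 20 patients per clinic and an intraclass correlation of 0.05 assumed, 1,500 replicates, and one clinic-level 0/1 predictor with no true effect. At nominal 0.05:

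- The ML deviance test rejected in 0.051 of replicates, whatever the coding.
- The REML deviance test, without the ln det(X'X) term, rejected in 0.010 with 0/1 coding, 0.175 with the predictor multiplied by 0.1, 1.000 multiplied by 0.01, and 0.0007 multiplied by 10.
- In one null data set the REML difference was −2.77 with 0/1 coding; the ML difference was 0.07.

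So with ordinary 0/1 coding the misuse was conservative in this setting; inflation came from shrinking the predictor's scale. The direction of error is not fixed.

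**2. Where a unit choice could arise.** Table 2 in Section 3.5 lists eight outcomes: five rates and three times in days. The times have a fixed unit. A rate has an open unit only if it is analysed as an aggregate. Table 2 lists provider, clinic and organization levels, but the equations in Section 4 are written for a patient's outcome, and a patient-level 0/1 outcome has no proportion-or-percent choice.

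**3. What the plan actually directs.**

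| Step in Section 4 | What changes | How the plan judges it |
|---|---|---|
| Unconditional models | Random terms only; one fixed intercept once written out | Inside the stated REML limit |
| Separate phase models | Fixed effect of a phase | From the coefficient estimate; valid under REML |
| Grand model | Three phase effects | Test not specified |
| Mediator, product term | Fixed terms added (the interaction example also adds a random slope) | Test not specified |
| Closing deviance test | Pairs not named | Follows directly after the sentence giving the REML limit |

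No row directs a REML deviance comparison across different fixed effects. Where the test is unspecified, the quantity of interest is a coefficient or a set of coefficients, and a test from the REML estimates is available.

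**The case for a change.** The strongest case for a change is one of order. The unconditional models, where a REML variance test is plainly valid, come at the start, whereas the likelihood ratio test comes at the end, when most of what has been added is fixed effects. If the test covers variance components only, Section 4 names no joint test for the grand model, although Objective 3 wants that model to test overall effectiveness. The printed interaction example also leaves out the clinic effect and adds a random slope, so neither it nor the printed predictor model contains the other, and calling the models nested does not identify a pair.

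The omissions are real: pairs, ML fit and restriction are all unstated. The inference from them is weaker. Section 4 does not tie the closing test to the grand model, mediation or interaction, and Objective 3 does not ask for a joint test with three degrees of freedom. If one is wanted, the three coefficients can be tested together from the REML fit. The two printed models are separate illustrations and are not offered as a comparison. The printed statistic is plain −2 log L, and the text neither states nor excludes an ML fit for it. An open scope is not an instruction to exceed a limit stated one sentence earlier.

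**Conclusion.** The concern does not call for a change. The algebra is right, and the misuse it describes would be serious: each shift in the table exceeds its own critical value. But the misuse is conditional throughout. It needs an analyst to override the plan's own correct statement about REML, and the proportion-to-percent example also needs aggregate rate models that Section 4 does not write out. A shift larger than the critical value does not by itself show a changed decision, because the starting level depends on the data and can be negative.

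The tests of the added components rest on coefficient estimates and are untouched. What remains is unstated detail about which pairs the closing test covers and how they are fitted. Analysts fill that gap in a standard way: REML deviances for pairs with identical fixed effects, allowing for the boundary when a variance is tested; and, where fixed effects differ, Wald or F tests with small-sample degrees of freedom, or ML fits to the same records. This conclusion assumes that the analyst applies the limit the plan states; nothing in the documents points the other way.

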3.5 Data Sources

During the first three months, we will work with the Quality Improvement Department at each partner site to collect baseline data on primary outcomes through the existing electronic medical record or chart reviews. After we start implementing the multilevel intervention, we will collect primary outcome data each quarter until the completion of the 4-year study period. Table 2 summarizes the primary outcome measures.

Table 2. Outcome Measures for the Multilevel Intervention

Outcome	Operational Definition	Data Sources	Data Collection Period	Level of Data Analysis
Patient CRC screening rates	Numerator: # of patients completed CRC screening Denominator: # of patients eligible for CRC screening	• EMR • Chart reviews as needed	Every quarter	Level 2, Level 3, Level 4
CRC ordering rates	Numerator: # of patients received order for CRC screening Denominator: # of patient eligible for CRC screening	• EMR • Chart reviews as needed	Every quarter	Level 2, Level 3, Level 4
Patient notification rates (FOBT/FIT +)	Numerator: # of patients notified Denominator: # of patients had FOBT/FIT +	• EMR • Chart review as needed	Every quarter	Level 2, Level 3, Level 4
Time to notification of positive results	# of days between notifying a patient with a positive result and the result available to the provider	• EMR • Chart reviews as needed	Every quarter	Level 2, Level 3, Level 4
Follow-up diagnostic evaluation referral rates	Numerator: # of patients received referral for evaluation Denominator: # of patients had FOBT/FIT +	• EMR • Chart reviews as needed	Every quarter	Level 2, Level 3, Level 4
Time to referral for follow-up diagnostic evaluation	# of days between the referral and the result available to the provider	• EMR • Chart reviews as needed	Every quarter	Level 2, Level 3, Level 4
Follow-up diagnostic evaluation completion rates	Numerator: # of patients completed diagnostic evaluation as ordered Denominator: # of diagnostic evaluation referral made	• EMR • Chart reviews as needed	Every quarter	Level 2, Level 3, Level 4
Time to completed diagnostic evaluation	# of days between the positive FOBT/FIT result available to the provider and the completion of the diagnostic evaluation	• EMR • Chart reviews as needed	Every quarter	Level 2, Level 3, Level 4

* Level 2 = Provider level; Level 3 = Clinic level; and Level 4 = organization level.

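### Eight outcomes are all primary and are tested by phase and overall at 0.05 with no lead outcome, hierarchy or adjustment, so the error rate across the primary outcomes is well above 5%

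*Combined protocol and SAP*

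**What the plan says.** Section 3.5 (Data Sources) states "Table 2 summarizes the primary outcome measures". Table 2 has eight rows, running from the patient screening rate to the time to completed diagnostic evaluation, defined as the number "of days between the positive FOBT/FIT result available to the provider and the completion of the diagnostic evaluation". No row is ranked above another and none is called secondary.

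Objective 3 (Section 2.1) sets out two kinds of model. The purpose of the grand model is given as: "test the overall effectiveness of the multilevel intervention on primary outcomes within and across levels". Phase-specific models are then added to it, in these words: "as well as separate models to assess effectiveness at each phase". Section 4 (Data Analyses) carries this out. First, "each intervention effect at each time phase will be estimated separately using linear-mixed effects models". These estimates are tested, not only described: "The estimate of intervention effect in each model will be used to test if additional intervention component significantly affects outcome measures". Then "we will develop a grand model including all three intervention effects simultaneously".

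Section 4 closes with the only rule on error rates: "the significant level will set at alpha ≤ 0.05". It does not say whether tests are one- or two-sided. No section gives a lead outcome, a testing order, an alpha split, a multiplicity adjustment or a rule for overall success. The summary at the front lists a somewhat different set of outcomes without calling them primary, so it does not narrow the primary set.

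**The concern.** A significance level of 0.05 limits the error of one test. Here it applies to at least eight primary outcomes, and to more tests once the phase models are counted. Because the plan does not say which result decides the question, nothing in it stops one significant outcome or phase from being reported as effectiveness on a primary outcome. The chance that such a report is false when no component works is then larger than the 5% a reader would take from the plan. This bears on the purpose given in Section 1.2, which is to supply an evidence base for multilevel interventions.

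**Working it through.** The plan gives no sample size, power or family-wise error figure, so there is nothing of its own to reproduce. The only stated figure is 0.05 per test.

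**Inputs**
- Per-test level: 0.05 (Section 4).
- Primary outcomes: 8 (Table 2, Section 3.5).
- Phase models: 3 per outcome (Section 2.1, Objective 3; Section 4).
- Overall test: 1 per outcome, taking Objective 3 to mean one overall test. Section 4 does not define it.
- Correlation between tests: not in the documents; assumed 0, 0.5 and 0.8.
- Every null hypothesis true, and each test holding its nominal 5%.

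**Number of tests**
- One overall test per outcome: 8 × 1 = 8.
- Three phases plus one overall: 8 × (3 + 1) = 32.

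**Independent tests**, chance of at least one false positive = 1 − (1 − 0.05)^m:
- m = 8: 1 − 0.95^8 = 0.337.
- m = 32: 1 − 0.95^32 = 0.806.

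**Correlated tests.** Two-sided z tests were simulated (200,000 draws), each statistic being √r × (shared normal) + √(1 − r) × (own normal), rejected beyond ±1.96.

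| Tests | r = 0 | r = 0.5 | r = 0.8 |
|---|---|---|---|
| 8 | 34% | 25% | 16% |
| 32 | 81% | 52% | 26% |

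**Second structure for the 32 tests.** An overall test partly repeats the phase tests. If it is built as the standardized sum of three independent phase tests (100,000 draws), the chance is 75% at outcome correlation 0, 62% at 0.5, 51% at 0.7 and 35% at 0.9.

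**Cost of Holm's procedure**
- First step: 0.05 / 8 = 0.00625, two-sided critical value 2.734 (against 1.960 at 0.05).
- Lone true effect with 80% power at 0.05: expected z = 1.960 + 0.842 = 2.802; power at the first step = Φ(2.802 − 2.734) = Φ(0.068), about 53%.
- With 90% power at 0.05: expected z = 1.960 + 1.282 = 3.242; Φ(3.242 − 2.734) = Φ(0.508), about 69%.

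The 80% and 90% are illustrative, since the documents contain no power calculation.

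**The case against.** The strongest reply is that the outcomes are steps in one care process and are unlikely to be independent. Screening and ordering rates share a denominator, notification and referral rates share another, and several time measures start from the same result date. This stands as a caution against the independence figures, and it is why a range is shown. It does not bring the rate near 5%: eight tests correlated at 0.8 still give 16%, about three times the stated level. Very high correlation should not be presumed either. Two rows concern patients eligible for screening, and the other six concern follow-up after a positive FOBT/FIT.

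A second reply is that each row is a distinct step that could support its own claim, and that the phase tests answer separate questions. That is a defensible position, but the plan does not take it: it gives all eight the same primary status and ties them to one effectiveness objective. Setting the phase tests aside leaves 16% to 34%.

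Three stronger readings are tempting, and the documents do not support them:
- A reader might infer that a false positive is more likely than not. That holds only for the full set of phase and overall tests under independence or moderate correlation. It fails under strong correlation, and it fails with one test per outcome.
- A reader might infer a separate 0.05 test at provider, clinic and organization level. Table 2 has a column of analysis levels and Objective 3 mentions levels, but Section 4 describes multilevel models with provider and clinic random effects and specifies no test per level. The levels are therefore not counted here.
- A reader might infer that the plan adopts a rule under which any one significant outcome counts as success. It states no success rule. The problem is that nothing excludes such a reading.

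**Conclusion.** The concern holds in this form: eight primary outcomes, tested by phase and overall at 0.05 with no lead outcome, hierarchy or adjustment, give a chance of at least one false primary-outcome finding well above 5%. With one overall test per outcome the range is 16% to 34%. With 32 tests it is 26% to 81% under equal correlation from 0.8 down to 0.

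These figures rest on all nulls being true, on assumed correlations, and on each test holding its nominal size. The last is itself uncertain, with four randomized FQHCs and random effects only for provider and clinic, but that is a separate matter. The simulated figures assume two-sided tests; the independence figures do not depend on sidedness. The weakness affects how results may be claimed, not how the trial is conducted.

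**What to change.** Add one paragraph to Section 4.

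1. Define one overall intervention contrast per outcome in the grand model, for example a joint test of the three intervention effects. Without it there are three coefficients per outcome, so 24 candidate p-values rather than eight. The paragraph should also name the test, because the section itself says that REML supports only comparisons of models differing in their variances.
2. Then choose one of two routes:
   - name one Table 2 outcome as the lead primary outcome, tested at 0.05, with the other seven secondary; or
   - keep all eight as primary and apply Holm's procedure across the eight overall tests. Holm needs no assumption about correlation, only that each test holds its size.
3. Report phase-specific results, and any level-specific ones, as supportive estimates with intervals and without significance claims.

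No outcome is dropped and data collection does not change. Under Holm the smallest p-value must be at or below 0.00625, with the power loss shown above (80% to about 53%, 90% to about 69%, for a lone true effect). Naming a lead outcome spares that outcome the loss, at the price of making claims on the other seven secondary.
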